**Additional Safety Observations:**

The frequency and severity of adverse clinical events and serious adverse clinical events will be assessed to determine if the use of open NIRS data bi-frontal cerebral monitoring is associated with any significant change in the observation of such events.

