- 4) Assess the interventional cohort's preoperative demographics and collected covariates for association with the ease or difficulty of mitigating observed cerebral desaturation events.

Exploratory analyses will include performing all possible comparisons of the two groups based upon all collected perioperative variables to examine the potentially significant relationships between the collected clinical variables representing surrogates of organ perfusion/function and cerebral oximetry desaturations (AUCrSO2). The following exploratory endpoints will be assessed:

- Logistic regression analysis to determine the most relevant AUCrSO2 desaturation value(s) associated with any detrimental clinical outcome(s) monitored in this study
- Logistic regression analysis to determine the most relevant AUC blood pressure values associated with any detrimental clinical outcome(s) monitored in this study
- Comparison of baseline rSO2 values (room air and oxygen supplemented) to all collected clinical variables to assess for possibly significant associations
- Explore the potential impact of rSO2 monitoring on changing the surgical conduct of the procedure

**Methodology:** Single center, prospective, randomized, controlled clinical pilot study

**Number of Subjects:** 100 subjects with balanced randomization (1:1) to control (blinded NIRS data) or intervention (open NIRS data) cohorts

**Main Criteria for Inclusion:** Elderly patients (> 65 years of age) scheduled for a thoracic surgical procedure at UHCMC that will involve SLV.

**Duration of Treatment:** Cerebral oximetry monitoring will begin with an assessment of both room air and oxygen supplemented bi-frontal baseline NIRS values and continue through the surgery to either PACU discharge or the initial 12 hours of post surgical ICU treatment. Mini Mental Status exam testing and Delirium testing with the Confusion Assessment Method will occur preoperatively and postoperatively through post-operative day (POD) #3 (or discharge if that occurs sooner than POD #3).

Enrolled subjects will be followed during the index hospitalization and will undergo a 30 day follow up telephone interview to assess their progress following hospital discharge.

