### **6.3 Secondary Objectives**

Secondary objectives of this pilot study include the following:

- 1) Assess the frequency of cerebral desaturations in both the intervention and control cohorts by examining both the total number of patients experiencing any cerebral desaturation as well as the total number of events among patients experiencing any cerebral desaturation (of at least 5% below baseline and progressively larger desaturations). These analyses will be conducted on the entire study population as well as upon each cohort. The Area Under the Curve (AUC) analysis

technique [incremental desaturation categories will be assessed based upon 5 to 50% decreases, measured in 5% increments, from established room air baseline as well as oxygen supplemented pre-incision baselines as well as desaturations below absolute measured rSO2 values] will be employed to conduct these analyses.

- 2) Assess the frequency of adverse clinical events and serious adverse events overall and in each cohort.
- 3) Perform a comprehensive assessment of the frequency and efficacy of predefined rSO2 desaturation mitigation interventions and their collective ability to affect the observed cerebral oximetry values.
- 4) Assess the interventional cohort's preoperative demographics and collected covariates for association with the ease or difficulty of mitigating observed cerebral desaturation events.

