# 9 SUBJECT SELECTION

## 9.1 Study Population

A total of 100 evaluable subjects will be enrolled into this protocol. Patients at least 65 years of age who are scheduled to undergo non-emergent, thoracic surgical procedures planned to involve the use of single lung ventilation will be evaluated in this study.

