### 12 TRIAL SAFETY

#### 12.1 Expert Clinician Unbiased Trial Safety Assessment

This trial will not employ a data safety monitoring board as three clinical trials with a similar design, sicker patients and larger (n) values have been previously conducted using the same cerebral oximetry device without evidence of safety concerns. (Ref Casati, Murkin, Slater) Instead, there will be two planned interim assessments of the collected adverse event data that will be reviewed by a clinical expert in the care of thoracic surgical patients as well as in clinical trial design and execution. [name], M.D. of the Department of Anesthesiology at Duke University School of Medicine will perform a review of collected adverse event data after enrollment of 25 subjects and 50 subjects. If [name] has concerns additional analyses will be performed on the collected clinical data to determine if any real safety issues exist for the subjects participating in this trial. [name] will provide a report to detail his conclusions and recommendations based upon the data he reviews. This data will be shared with the UHCMC IRB.

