## **15 STATISTICAL PLAN**

All collected data in the case report form will be transferred into a customized electronic database upon completion of the study for the purpose of facilitating statistical analysis.

Preoperative demographics and clinical variables will be compared in the two groups to assess for significant differences using the independent t-test. Differences in the observed clinical data between groups will be determined with the Wilcoxon rank-sum test. Stepwise, forward, multivariable logistic regression analysis will be performed to assess for relationships between cerebral desaturations and any of the measured clinical variables with a p value < 0.05 being considered significant.

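### The end-of-study adverse event comparison is posed as a significance question with no interval or harm margin, and at 50 per arm a non-significant answer says little about uncommon serious events

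*Combined protocol and SAP*

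**What the plan says.** The Synopsis, under Additional Safety Observations, gives the purpose of comparing AEs and SAEs between arms: "to determine if the use of open NIRS data bi-frontal cerebral monitoring is associated with any significant change in the observation of such events". Section 6.3 lists a related secondary objective without significance wording: "Assess the frequency of adverse clinical events and serious adverse events overall and in each cohort".

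Section 15, which repeats the statistical paragraph of the Synopsis, has no analysis specific to AEs. Its only general method for outcome comparisons is this: "Differences in the observed clinical data between groups will be determined with the Wilcoxon rank-sum test". The one threshold, "with a p value < 0.05 being considered significant", closes the sentence on stepwise logistic regression. Neither place mentions a confidence interval, a harm margin, a detectable excess or a sidedness.

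On size, the Synopsis has "100 subjects with balanced randomization (1:1) to control (blinded NIRS data) or intervention (open NIRS data) cohorts", and section 9.1 has "A total of 100 evaluable subjects will be enrolled into this protocol".

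Three other provisions bear on safety: external expert review of AE data after 25 and 50 subjects (section 12.1), review and causality assessment of each event with SAE reports shared with the IRB (section 13.2), and the per-cohort frequencies of section 6.3.

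**The concern.** A question about whether a comparison "is associated with any significant change in the observation of such events" has two natural answers: yes, or no significant change. In arms of 50 the second is the likely answer for an uncommon event, even if the intervention doubles its rate. Nothing in the plan would show how large an excess is still compatible with the data.

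The difference between arms is a genuine question here. Under section 10.3 only the intervention arm follows the desaturation algorithm, which can lead to fluid, vasoconstrictors, carbon dioxide targets, inotropes and transfusion. At stake is what the pilot can say about harm when it ends. With a p value alone, it cannot separate a result that rules out a large excess from one that is merely imprecise.

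**Working it through.** **Plan's own figure.** There is none. The documents give no power, sample-size basis, expected event rate or harm margin.

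**Inputs**
- Arm size: 100 subjects at 1:1, so 50 per arm (Synopsis, section 9.1).
- Test: rank-sum on a yes/no outcome (subject had an event or not). Assumed; section 15 assigns this test to clinical data in general and does not mention AEs.
- Alpha: two-sided 0.05. Assumed; the 0.05 is attached to the regression, and no sidedness is stated.
- Control event rate: assumed, 2% to 30%.
- Effect: a doubling of the proportion with an event. Assumed, as a benchmark.

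**Formula.** Let a of n control subjects and b of n intervention subjects have an event, with n = 50 and p = (a + b)/(2n). For yes/no data the rank-sum statistic is

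Z = [(b − a)/n] / √[p(1 − p) × 2/n] × √[(2n − 1)/(2n)],

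and the test rejects when |Z| > 1.96.

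**What significance would take.** Suppose 5 of 50 controls (10%) have an event.
- 12 intervention events: p = 0.17, Z = 0.14/√(0.17 × 0.83 × 0.04) × √0.99 = 1.85, not significant.
- 13 intervention events: p = 0.18, Z = 0.16/√(0.18 × 0.82 × 0.04) × √0.99 = 2.07, significant.

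So 24% against 10% would still count as no significant change.

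**Chance of missing a doubling.** Sum the binomial probabilities of every (a, b) pair for which the test does not reject:

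| Control v intervention | Missed, rank-sum | Missed, Fisher's exact |
|---|---|---|
| 2% v 4% | 94.6% | 99.4% |
| 5% v 10% | 85.6% | 93.7% |
| 10% v 20% | 72.0% | 80.5% |
| 15% v 30% | 56.1% | 64.6% |
| 20% v 40% | 40.5% | 48.5% |
| 25% v 50% | 25.5% | 32.5% |
| 30% v 60% | 12.4% | 17.1% |

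**Sensitivity (normal approximation).**
- A one-sided 0.05 test at 50 per arm misses 75.8% at a 5% control rate and 29.1% at 20%.
- With 40 per arm, two-sided, the figures are 86.8% and 50.3%, against 84.5% and 41.0% at 50 per arm.

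**What an interval would show.** The Newcombe method builds the interval from the Wilson limits (l, u) of each arm. With d the intervention minus control difference, and subscripts I and C for intervention and control:

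lower = d − √[(p_I − l_I)² + (u_C − p_C)²]; upper = d + √[(u_I − p_I)² + (p_C − l_C)²].

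The Wilson 95% limits are 4.35% to 21.36% for 5/50 and 11.24% to 33.04% for 10/50.
- 5/50 v 5/50: d = 0, and √(11.36² + 5.65²) = 12.7, giving −12.7 to +12.7 percentage points.
- 10/50 v 5/50: d = 10, lower 10 − √(8.76² + 11.36²) = −4.3, upper 10 + √(13.04² + 5.65²) = +24.2. The rank-sum p value is 0.16.

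Both results would be reported as no significant change, yet one leaves an excess of about 13 points open and the other about 24.

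**The case against.** The strongest reply is that the documents never say a non-significant result will be taken as absence of harm. That is correct. A reader might infer such a rule from the Synopsis wording, but the text states an aim and does not say how a negative answer will be reported.

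A reader might also infer that safety rests on this comparison alone. It does not. The expert review in section 12.1 is prompted by clinical concern, not by a p value: if the expert has concerns, "additional analyses will be performed on the collected clinical data to determine if any real safety issues exist for the subjects participating". No interim significance test is planned, so the miss rates above do not apply to those reviews. Section 13.2 covers individual events, and many plausible harms, such as transfusion, stroke, ischemia and renal change, are collected as named outcomes in both arms. These provisions stand, but none states how precisely the trial will know the difference between arms at the end.

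Third, the miss rates depend on assumed control rates. That also stands. Section 13.1.1 defines an AE broadly enough to include abnormal laboratory findings, so the proportion with at least one AE could well exceed 20%. There the test does much better.

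Finally, low power for uncommon harms is common to small pilots, and per-cohort frequencies would let a reader compute an interval unaided. This is a reason to plan estimation. It does not call for more subjects, and it does not remove the need to change a question worded around significance.

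**Conclusion.** The point holds as one about how the end-of-study comparison is framed and what it can show. The AE and SAE question is put in terms of significance, and the plan supplies tests without an interval or margin. At 50 per arm a doubling would be missed about 86%, 72%, 56% and 40% of the time at control rates of 5%, 10%, 15% and 20%. The figure is about 95% at 2%, and falls to about 25% and 12% at 25% and 30%. A negative answer is therefore weak evidence about uncommon SAEs and more informative about common AEs.

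These figures rest on assumed event rates, a doubling as the benchmark, a rank-sum test on yes/no data and two-sided 0.05. Fisher's exact test misses more; a one-sided test misses less.

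Three stronger conclusions are not supported: that the investigators will declare the intervention harmless on a non-significant test, that no other safety oversight exists, or that any one range of miss rates applies whatever the event rate. Nor do the documents give the pilot's safety statement a role in a device indication. Section 6.2 assigns the definitive demonstration to the later multicentre trial.

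**What to change.** In the Synopsis (Additional Safety Observations) and in section 15, replace the significance question with estimation:

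- For subjects with at least one AE, and separately at least one SAE, report the number and proportion per arm and the risk difference (intervention minus control) with a two-sided 95% Newcombe or Miettinen-Nurminen interval.
- State the upper limit of each interval as the largest excess that the pilot cannot exclude.
- State that a non-significant difference is not evidence of no harm.

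This needs no new data and no additional subjects. It costs a wording change in two places and one extra table. The downside is a visibly less reassuring safety statement: even with identical counts of 5 in each arm, the report would have to say that an excess of up to 12.7 percentage points has not been ruled out.

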**Statistical Methods:**

Preoperative demographics and clinical variables will be compared in the two groups to assess for significant differences using the independent t-test. Differences in the observed clinical data between groups will be determined with the Wilcoxon rank-sum test. Stepwise, forward, multivariable logistic regression analysis will be performed to assess for relationships between cerebral desaturations and any of the measured clinical variables with a p value < 0.05 being considered significant.

#### 4 LIST OF ABBREVIATIONS AND DEFINITIONS OF TERMS

AE	Adverse Event
AUC	Area Under the Curve
CAM	Confusion Assessment Method test
CI	Confidence Interval
CWRUSOM	Case Western Reserve University School of Medicine
GCP	Good Clinical Practices
H-LOS	Hospital Length of Stay
ICU	Intensive Care Unit
MMSE	Mini Mental Status Examination
MOMM	Major Organ Morbidity and Mortality
NIRS	Near Infra-Red Spectrophotometry
OR	Odds Ratio
POD	Post Operative Day
rSO 2	Regional Oxygen Saturation (frontal lobe)
SAE	Serious Adverse Event
SLV	Single Lung Ventilation
STS	Society of Thoracic Surgeons
UHCMC	University Hospitals Case Medical Center

## 5 Background and Rationale

### 5.1 Introduction

This protocol is a pilot study designed to assess the clinical impact of the intraoperative and immediate postoperative use of regional, near infra-red spectrophotometric (NIRS) monitoring using the INVOS® 5100 to assess bi-frontal cerebral oxygenation in elderly thoracic surgical patients undergoing procedures involving single lung ventilation (SLV). We seek to determine the impact of NIRS bi-frontal monitoring on any relevant clinical variables in the selected patient population in order to most efficiently design a multicenter, prospective, randomized controlled trial to definitively describe the potential clinical impact of this monitoring modality in the postoperative period.

This study will be conducted in compliance with Good Clinical Practices (GCP) including the Declaration of Helsinki and all applicable regulatory requirements.

### 5.2 Background

Cerebral oximetry monitoring has been in clinical use for over thirty years and has been commercially available to clinicians for over two decades. (Jobsis FF) The use of specific wavelengths of near infrared light along with an understanding of the Lambert-Beer Law permits determination of a regional, venous weighted saturation (75% venous : 25% arterial with the INVOS® device) of tissue beneath the sensor. Specifically, the device is measuring the percentage of oxygenated hemoglobin in blood vessels less than 100 microns in diameter (i.e. the exchange vessels including arterioles, capillaries and venules). (Avery EG) The venous weighted nature of the measurement allows for the determination of the oxygen balance within the interrogated tissue. For example, desaturated tissue will have lower regional saturation values as a result of decreased oxygen delivery and/or increased oxygen extraction.

### 5.3 Clinical Studies

Since this technology was made commercially available to practitioners several clinical studies including prospective, randomized controlled trials, both prospective and retrospective observational studies as well as a number of case reports have been published that support the use of NIRS-based cerebral and somatic tissue oximetry in surgical and critically ill patients. These clinical studies have been conducted in diverse groups of surgical patients which have demonstrated clinically beneficial outcomes for subjects who were monitored with this technology along with the implementation of standardized interventional algorithms designed to mitigate any observed desaturations. Among the patient groups that have been studied are general, vascular, adult cardiac, pediatric cardiac, adult thoracic surgical and neurocritical care patients. (Casati A et al, Murkin JM et al, Slater JP et al, Kasman N et al, Tang L et al) The use of these devices has been associated with improved clinical outcomes (decreased intensive care unit (ICU) and hospital length of stay (LOS), decreased stroke, decreased incidence of well accepted composite endpoints [i.e. the Society of Thoracic Surgery (STS) Major Organ Morbidity and Mortality (MOMM) composite endpoint that includes death, stroke, renal dialysis, surgical re-exploration, prolonged ventilation and mediastinitis] as well as decreased incidence of neurocognitive dysfunction) in observational studies as well as in prospective, randomized controlled trials which suggests more than an associative relationship between the use of NIRS cerebral monitoring and these improved outcomes.

Active testing of this technology over the past decade has brought forth the concept that by placing the sensors over the frontal lobe cerebral tissue and actively working to reverse the observed desaturations clinicians are very likely protecting the oxygen balance in all of the body's vital organs by using the brain as an index organ of adequate perfusion and oxygenation. (Grocott HP) Indeed, the improved clinical outcomes that have been published in the peer reviewed literature suggest a diffuse effect of generalized organ protection (e.g., decreased hospital LOS, decreased ICU LOS, decreased STS MOMM). It appears that despite the regional nature of the small amount of tissue that is monitored (i.e. 15 mm^3 of frontal lobe cortical gray matter) that this highly metabolically active cerebral tissue may be the most desirable tissue to assess and use as an index organ for providing adequate oxygen balance in the rest of the body.

Clinicians caring for perioperative cardiac surgical patients (e.g., cardiac anesthesiologists, cardiac surgeons and perfusionists) were early adopters of this technology related to the compromised cardiovascular status inherent to their patient population and the complex nature of the surgical procedures they perform (e.g., extracorporeal circulation and deep hypothermic circulatory arrest).

### **Study Rationale**

There are presently two prospective, randomized controlled trials which strongly support the notion that these devices improve perioperative clinical outcomes in surgical patients as well as a large number of observational studies which strengthen the association of the use these devices to improved outcomes. (Murkin JM et al, Cassati A et al, Goldman S et al, Heringlake M et al, Schoen J et al) However, there is only one published observational study performed to date involving the use of NIRS-based regional cerebral oximetry of thoracic surgical patients undergoing SLV. That study only assessed the association of NIRS-based cerebral oximetry to postoperative neurocognitive dysfunction and did find a positive relationship between observed cerebral oximetry data and postoperative cognitive dysfunction (i.e. 29% of patients had significantly decreased Mini Mental Status Exam scores at 3 hours postoperatively and a ↓rSO2 <65% for even just 5 minutes was associated with ↑OR 2.03 [95% CI: 0.74 – 5.59]) for developing early neurocognitive dysfunction. (Tang L)

Elderly thoracic surgical patients undergoing SLV related procedures were not included in any of the prospective randomized controlled trials and only the single, small observational study referenced above assessing postoperative neurocognitive dysfunction exists to test the hypothesis that NIRS based bifrontal cerebral monitoring has the potential to affect any clinical outcome in this subpopulation of surgical patients. Further, NIRS based bi-frontal cerebral monitoring is not accepted as a standard of care in thoracic surgical patients which permits the employment of randomized, controlled testing methodology in this patient population.

The establishment of cause and effect in clinical medicine is largely dictated by the conduct of multicenter, prospective, randomized controlled trials. This pilot study is intended to define the optimal clinical endpoints and statistical design needed to establish the potential benefits of NIRS based bi-frontal regional cerebral oximetry monitoring in elderly thoracic surgical patients undergoing procedures involving SLV.

This pilot study involves the collection not only of cerebral oximetry data but also of blood pressure and pulse oximetry data as well as a number of clinically relevant outcome measures that can reflect the adequacy of organ protection during the intraoperative and immediate postoperative period. Having serial

blood pressure and pulse oximetry data will allow for any possible correlations that exist between these standard physiologic parameters and the observed clinical outcomes to be assessed as it has been previously established that blood pressure control is associated with clinical outcomes in cardiac surgical patients (Weir M et al). Further, by collecting this data it will be possible to quantify the relative strength of any potential correlations of these standard physiologic parameters as well as cerebral oximetry data to the observed clinical outcomes potentially permitting a direct comparison of how useful optimizing these parameters may be in the postoperative period. Finally, we will potentially be able to establish the effect of blood pressure variability on observed cerebral oxygen balance in a real time clinical environment which could reveal that commonly used perioperative blood pressure goals alone are inadequate measures to optimally protect vital organs in our study population. A series of clinical experiments assessing cerebral autoregulation has recently been published by Dr. C. Hogue's group which strongly suggests that by using conventional medical approaches clinicians may do a poor job of predicting the lower limits of cerebral autoregulation and providing adequate cerebral blood flow in patients with advanced cardiovascular disease undergoing procedures involving the use of cardiopulmonary bypass. (Joshi B et al.) Our study has the ability to help solidify [name] findings which suggest that widely accepted discretionary blood pressure goals (e.g. maintaining mean arterial pressure within 20% of the preoperatively observed values) may not be adequate for optimal cerebral protection.

